DilaCheck® Trial

TITLE:

**Inter-examiner Agreement of a Novel Device for the Measurement of Cervical
Dilation in Labor: A Randomized Controlled Trial**

NCT Number: 03440723

Date of the Document: January 1, 2019

PROTOCOL

TITLE: Inter-examiner Agreement of a Novel Device for the Measurement of Cervical Dilatation in Labor: A Randomized Controlled Trial

ABBREVIATED TITLE: DilaCheck® Trial

PROTOCOL SUMMARY

Measurement of cervical dilation during late pregnancy and labor informs decisions in the management of labor and delivery. Prior published research suggests that practitioners are only 48 to 56% accurate when judging cervical simulators.¹⁻³ When measuring laboring women, two practitioners' measurements agree only 49% of the time.⁴ [name] of Elm Tree Medical Inc. (the Sponsor) developed a novel device, DilaCheck®, to enable practitioners to increase accuracy in cervical dilation measurements.

Elm Tree Medical completed a preliminary trial using a simulator similar to those used in prior studies. Fifty Labor and Delivery practitioners completed examinations using standard methods and then the device. Standard methods yielded an accuracy of 46%. With the device, accuracy increased to 96%, representing an 108% increase. The device was equally accurate regardless of years of experience or level of training. Standard methods resulted in a 10.5% rate of errors of two or greater centimeters from the true value. The device eliminated readings that were incorrect by more than one centimeter.

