Eligibility. Subjects eligible for inclusion in the study must be: pregnant women who are admitted to a Labor and Delivery unit for management or induction of labor in the first stage of labor, are able to give informed consent, are 18 years of age or greater, English-speaking, have intact membranes, and have a gestational age greater than or equal to 37 weeks (i.e. term pregnancy). Inclusion criteria also include having a functioning epidural in place or having provided consent prior to the start of labor. Exclusion criteria include progression to the second stage of labor (i.e. known dilation of ten centimeters), non-English speaking, known prior rupture of membranes, any condition that renders labor unsafe for the patient (e.g. cardiac conditions, pulmonary hypertension) and any other condition that necessitates an emergent or urgent cesarean section (e.g. non-reassuring fetal status, placental abruption, hemorrhage, cord prolapse). Patients are only consented if they have adequate pain control, either because they are not yet in labor (i.e. are admitted for an induction of labor) or have a functioning epidural. All participants are necessarily female due to the subject matter. Given the vulnerability of pregnant patients under the age of 18, this study will exclude children. There are no restrictions on eligibility based on race or ethnicity. Patients can withdraw from participation at any point in the study. DilaCheck® is FDA-cleared for use by qualified healthcare professionals for women in pregnancy and labor without any further restrictions.

Provider Enrollment. The Sponsor, TJU Principle Investigator, or trial coordinator will discuss participation in the trial with providers at the TJU Labor and Delivery unit. Providers will be given the option of participating on a volunteer basis.

Provider Training. The Sponsor will train participating providers in the use of the device. The Sponsor will use a detailed script to ensure standardization of the training. The Sponsor will use a wooden cervical simulator box to train providers to use the study device without patient involvement. The standardized training will test competency with the device using the cervical simulator. The providers will also have access to a training video to reinforce the in-person training.

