For participants in the DilaCheck® arm, the subjective and DilaCheck®

DilaCheck® Trial

measurements will be plotted along an X-Y axis and the Pearson correlation coefficient between the two data sets will be calculated. This analysis will be completed for both the fractional and integral (non-fractional) sets of DilaCheck® measurement readings.

The photographs of the DilaCheck® measurements will be read by an independent, blinded reviewer to report the DilaCheck® measurements. The provider's and reviewer's DilaCheck® measurements will be plotted along an X-Y axis and the Pearson correlation coefficient between the two data sets will be calculated. This analysis will be completed for the fractional and integral (non-fractional) sets of DilaCheck® measurement readings.

The correlation between the providers' subjective and DilaCheck® measurements will be analyzed over time. To do so, for providers who complete at least 10 exams, the correlation of the two measurements in the provider's first half of examinations will be compared to the providers' second half of measurements. A T-test will be completed to determine whether the two correlations differ significantly. The analysis will be repeated for both the fractional and integral (non-fractional) sets of DilaCheck® measurement readings and using the data sets of readings from the independent reviewer.

The average pain score in each group will be calculated, and a Students T test will be performed to determine whether pain scores differed significantly between groups. Using logistic regression whether provider number, patient age, gestational age, weight, or epidural status significantly impacted likelihood of agreement or pain score within each group will be determined. The average provider confidence in accuracy will be calculated, and a Students T test will compare if patients' confidence differs significantly between groups. Logistic regression will be used to determine if provider experience or training significantly predicted likelihood of agreement.

Any additional statistical analysis appropriate for the data collected will be performed. For the qualitative data, including descriptions of adverse events and feedback, each of the responses will be reviewed individually. Any serious adverse events will be reported. Any informative feedback or themes in the feedback will also be collated.

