Potential Risks of Study Participation. The device is not anticipated to present any risk above that of a standard cervical dilation examination with a sterile glove. Potential risks to the patient include loss of confidentiality, discomfort with cervical examinations, a theoretical increased risk of infection, rupture of membranes, and inconvenience. For the provider, there is not anticipated to be any risk above that of performing a standard cervical dilation examination with a sterile glove.

Recruitment and Informed Consent. The sampling plan will ensure that all eligible patients are offered the opportunity to participate, regardless of race, ethnicity, or

socioeconomic status. The trial coordinator will consent patients in a private room or area. Consent will be documented with signatures of the trial coordinator and the patient on the Patient Informed Consent Form. Patients will receive a copy of the Patient Consent Form.

Randomization. Patients will be randomized to a treatment group using a computer-generated randomization program to eliminate assignment bias.

Confidentiality. Only the trial coordinator, the Sponsor, and the PI will have access to individually identifiable private information about human subjects. The hospital providers will likely have access to this information through the hospital medical record, but they will not be provided with the data through participation in the trial. The trial coordinator will store trial materials in a locked space at TJU. All physical materials obtained by Elm Tree Medical will be stored in a locked file at the Elm Tree Medical Inc. office. The trial coordinator will provide Elm Tree Medical with an electronic report of data collected. Any data entered into electronic form on TJU or Elm Tree Medical computers will be password-protected.

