Importance of the Knowledge to be Gained. The greatest benefit of the proposed research is the validation of a new device that could revolutionize labor management. If successful in increasing inter-examiner agreement, DilaCheck® has the potential to increase certainty in the management of labor, decrease length of admissions to the Labor and Delivery unit, decrease unnecessary interventions and cesarean sections, and decrease the time a woman is in labor. Since the device is not anticipated to expose patients to any significant risks, this potential for a vast benefit to laboring mothers and newborns far outweighs the risks to participants.

DATA AND SAFETY MONITORING PLAN

TJU IRB Review. We will submit a detailed monitoring plan to the TJU IRB for review and approval prior to initiation of the trial. All serious adverse events (AEs) will be reported to the TJU IRB within one week of the investigator becoming aware of the event. Any unanticipated problems will be reported to the TJU IRB within two weeks. The TJU IRB also requires interim reviews of the trial, either every six or 12 months, as determined by the IRB upon initial review of the protocol. The continuing review is submitted through completion of the "Continuing or Final Review of Research Protocols Involving Human Subjects" form. It includes enrollment data, adverse event reporting (including identification of adverse events not anticipated in the consent form), increased risks identified since the last review, demographics of enrolled patients, withdrawal of patients, loss to follow up, subject complaints, protocol changes, interim findings, assurance of an up-to-date literature review by the PI, changes to FDA status, and conflicts of interest. We will submit this form to the TJU IRB every six or 12 months, per the IRB's designation.

Sponsor Review. The Sponsor will review all data collected from the prior month at the beginning of each month. If there are serious AEs, she will report them to the necessary institutions.

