DSMB Review. The DSMB consists of four volunteer experts in the following fields: obstetrics, clinical trials, law, and ethics. Because they are volunteers, they do not stand to benefit from continuing the trial if it is not in the best interest of participants. The Sponsor will compile a document with enrollment data, lists of all adverse events, and summary statistics of data collected up to that date on a monthly basis. All information will be de-identified. The Sponsor will distribute the document via email to the members of the DSMB on the last Friday of each calendar month for the prior month's data. The DSMB members will review the document. If there are unexpected or serious AEs, the DSMB will determine whether continuation of the trial is safe. They will have the power to discontinue the trial at any time if they feel continuation is not in the best interest of patients. The Sponsor will be responsible for reporting a trial discontinuation due to safety concerns to the necessary regulatory bodies.

NIH/ Funding Institution & Center (IC). This trial has been accepted for funding from a STTR grant. The funding IC for this trial is the Eunice Kennedy Shriver National Institute of Child Health & Human Development (NICHD). The Sponsor will submit a monitoring plan to the NICHD Program Officer (PO) before the trial begins. During the trial, the Sponsor will inform the NICHD PO of any recommendations and activities that emanate from monitoring activities. The Sponsor will submit summary reports of the DSMB's discussions to the NICHD PO on a monthly basis as they become available. All

unanticipated problems and serious adverse events will be reported to the NICHD PO within one month of the IRB's receipt of the report of the problem from the Sponsor.

FDA. The FDA has cleared DilaCheck® as a Class 1 low risk device. The original device design was cleared by a 510(k) application. Because the current design represents such a low (non-significant) risk, it is considered Class 1 exempt and does not require FDA clearance of a 510(k) application prior to marketing. Pre-market obligations have been documented via a "Letter to File," and the device is registered with the FDA. The FDA has not withheld or restricted the device.

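### The device's developer sees all data monthly, with no arm masking stated, while the primary reading set, the rounding of control readings and added analyses stay open

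*Combined protocol and SAP*

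**What the plan says.** **Who sees the data.** The Protocol Summary says that a named individual "of Elm Tree Medical Inc. (the Sponsor) developed a novel device, DilaCheck". Under Sponsor Review: "The Sponsor will review all data collected from the prior month at the beginning of each month". The only action named there is the reporting of serious adverse events. Under DSMB Review, the sponsor compiles enrolment data, adverse events and "summary statistics of data collected up to that date on a monthly basis". The only protection given for that document is "All information will be de-identified". Under Confidentiality: "The trial coordinator will provide Elm Tree Medical with an electronic report of data collected", and "Only the trial coordinator, the Sponsor, and the PI will have access to individually identifiable private information about human subjects".

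**What else the sponsor does.** Under Provider Training: "The Sponsor will train participating providers in the use of the device". Photograph Review gives it the training of the photograph reviewer too. The paragraph after the missing-data rules has the sponsor giving site staff access to the analysis and the draft article for comment, which implies that the sponsor holds the analysis.

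**What the analysis leaves open.** Statistical Analysis fixes a two-sided 0.05 level, a t test, and three categories: any difference, one centimetre, and two or more. It applies them to both the fractional and the integer device readings and names neither as primary. Data Collection lets control examiners write whole or fractional values, with no rule for setting these against the integer device readings. The section then adds: "Any additional statistical analysis appropriate for the data collected will be performed".

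**The concern.** The party with the strongest interest in a positive result can watch the outcome data build up while the definition of the primary comparison is unsettled. De-identification does not hide the arm. A device record carries a photograph, a subjective reading and two device readings per examiner, whereas a control record carries one reading per examiner.

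Exact agreement depends heavily on how coarsely readings are recorded. If the reading set and the handling of fractional control values are settled once results are known, an apparent gain in agreement could come from the recording scale instead of the device. A reader of the final report could not tell the two apart.

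**Working it through.** The plan gives no error rate for this point, and its power calculation does not bear on it. The check asks how much the open scale could move the primary result.

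**Inputs from the plan:** 25 patients per arm, two-sided 0.05, t test on the proportion of patients whose two readings differ, integer or fractional device readings, integer or fractional control readings.

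**Assumptions, not in the plan:** true dilation uniform from 2 to 9 cm (1 to 9 cm gives nearly the same results); each reading equals the truth plus independent normal error with SD 0.4, 0.6 or 0.8 cm, the same in both arms, so the device has no advantage; all control readings are to the nearest half-centimetre.

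**Step 1. Exact agreement by recording scale, same precision (simulated):**

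| Error SD | Whole cm | Half cm | 0.1 cm |
|---|---|---|---|
| 0.4 | 56.6% | 33.1% | 7.0% |
| 0.6 | 42.2% | 22.9% | 4.7% |
| 0.8 | 33.0% | 17.4% | 3.6% |

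**Step 2. False significance, integer device readings against half-centimetre controls.** Power is approximately Φ(d/SE − 1.96), with SE = √{[p₁(1−p₁) + p₂(1−p₂)]/25}.

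- SD 0.4: d = 0.566 − 0.331 = 0.235; SE = √[(0.2456 + 0.2214)/25] = 0.137; d/SE = 1.72; Φ(−0.24) ≈ 40%.
- SD 0.8: d = 0.330 − 0.174 = 0.156; SE = √[(0.2211 + 0.1437)/25] = 0.121; d/SE = 1.29; Φ(−0.67) ≈ 25%.

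Summing the binomial probabilities over all outcomes where the t test gives p ≤ 0.05 yields 43% at SD 0.4, about 32% at 0.6 and 26% at 0.8. A simulated version can come out a point higher. Nearly all of these results favour the device.

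**Step 3. Same scale in both arms.** With half-centimetres in both arms the same sum gives about 5.5% at every SD. With whole centimetres in both it gives 5.5% to 6.3%. The small excess over 5% comes from using a t test on 0/1 data.

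**Step 4. Sensitivity to the control assumption.** Suppose both examiners use whole centimetres in half of the control patients. At SD 0.4, control agreement becomes 0.5 × 0.566 + 0.5 × 0.331 = 44.9%, and false significance falls to about 16%. At SD 0.8 it falls to about 10%.

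**Step 5. The other reading set.** Fractional device readings may take any fraction. If they were read to 0.1 cm, device agreement would be 7.0% to 3.6%, against 33.1% to 17.4% for half-centimetre controls. The two reading sets can therefore point in opposite directions with no true difference.

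**The case against.** **Repeated looks.** A reader might infer that monthly viewing inflates the type I error, as unplanned interim analyses would. The documents do not support this. No efficacy test or efficacy stopping rule is attached to the monthly review, and the DSMB's stated power to stop concerns the interest of patients. Nor do they say that the six comparisons (three categories by two reading sets) are run each month, or that the DSMB summaries are split by arm.

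**A two-test figure.** It is also tempting to price the viewing at 1 − 0.95² = 9.75%. That figure comes from having two reading sets, and both would be available at the final analysis without any monthly review. It is not an upper bound either: for two 5% tests the general bound is 2 × 0.05 = 10%, and the planned t test on 0/1 data already exceeds 5%.

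**Result-driven training.** A reader might also infer that the sponsor will retrain examiners in response to results. The text describes scripted training with competency testing, and feedback triggered by a fixed count of five device examinations and judged against the photograph reviewer, not against agreement by arm.

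**Existing safeguards.** The test, level and difference categories are fixed. The plan commits to analysing both reading sets, so reporting only one would depart from it. The photograph reviewer is called independent and blinded, and site staff may comment on the analysis. That the sponsor sees the arm and runs the analysis is inferred, though strongly, and not written.

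**What stands.** None of these safeguards says which reading set carries the conclusion or how control fractions are treated, and none separates the sponsor's view of the outcomes from those decisions.

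**Conclusion.** The point holds as one of governance and pre-specification. The text permits the headline comparison to be chosen with outcome data in view; it does not show that this happened or was intended. The monthly viewing carries no calculable error rate of its own. The size comes from the unmatched scales: about 43% to 26% false significance against about 5.5% when matched at half-centimetres. These figures rest on the assumed error SDs, normal independent errors and all-half-centimetre controls. They fall to about 16% to 10% if half of the control patients are read in whole centimetres, and further as that share rises. The scale problem would exist without the monthly review. The review matters because it lets an interested party see which choice looks better before making it. This is an inexpensive improvement and does not invalidate the design.

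**What to change.** 1. **Sponsor Review:** limit the monthly review to enrolment, adverse events, device failures, missing forms and protocol deviations. **DSMB Review:** give any dilation summary pooled over arms. Since device records reveal their arm, the coordinator should supply the pooled figure, and the electronic report under Confidentiality should follow the same limit until enrolment ends.
2. **Statistical Analysis:** before any by-arm readings are seen, name and date one primary reading set, state the rule that puts both arms on the same scale, and label the other set as secondary and any added analyses as secondary or post hoc. If by-arm readings have already been seen, say so and label these choices post hoc.
3. **Keep Continuous Feedback**, with the coordinator and the photograph reviewer matching the readings without the sponsor. Meet the interim-findings item in the IRB continuing review with pooled figures.

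The cost is mainly wording, plus a little coordinator time for the pooled figures and the feedback. The sponsor would learn of reading problems later, but Risks Related to the Study Device says that examination results do not enter patients' clinical care.

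### The only route to the DSMB that the protocol describes is a monthly email, 22 to 61 days after an event on the prior-month reading, with no individual notice of serious events

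*Combined protocol and SAP*

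**What the plan says.** All of this is in the Data and Safety Monitoring Plan of the combined protocol and SAP.

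- **DSMB Review, timing.** "The Sponsor will distribute the document via email to the members of the DSMB on the last Friday of each calendar month". The end of that sentence fixes the content: "on the last Friday of each calendar month for the prior month's data".
- **DSMB Review, content.** The preceding text describes the document as holding enrollment data, lists of all adverse events and "summary statistics of data collected up to that date on a monthly basis". Which date is meant is not defined. Everything sent to the DSMB is to be de-identified.
- **DSMB Review, task.** After the members review the document: "If there are unexpected or serious AEs, the DSMB will determine whether continuation of the trial is safe". Also: "They will have the power to discontinue the trial at any time".
- **Sponsor Review.** "The Sponsor will review all data collected from the prior month at the beginning of each month". Then: "If there are serious AEs, she will report them to the necessary institutions". The institutions are not listed and no time limit is given.
- **TJU IRB Review.** "All serious adverse events (AEs) will be reported to the TJU IRB within one week" of the investigator's awareness. Unanticipated problems go to the IRB within two weeks.
- **FDA.** Serious events are reported within one week if fatal or life threatening, and otherwise within 15 days.
- **NIH/Funding Institution and OHRP.** Serious events and unanticipated problems are reported within one month of the IRB receiving its report.

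**The concern.** The plan gives the continuation decision to the DSMB, and stresses that its members are volunteers with nothing to gain from continuing. It then sets a reporting clock for serious events to the IRB, FDA, NICHD and OHRP, but none to the DSMB. What the DSMB gets is a periodic summary that goes out at the end of the month after the one it covers, although the Sponsor has already looked at those data weeks before. No reason for the gap is given.

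The Human Subjects section says it is of great importance to study the device under strict monitoring for serious or unexpected events. Followed as written, the schedule lets enrollment go on for weeks before the body charged with the safety judgment learns of an event. In addition, the DSMB Review section describes the report's cut-off in two ways that do not obviously agree, so the DSMB cannot tell how current its document is.

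**Working it through.** The documents state no delay, so there is no figure of theirs to reproduce. The delay follows from the calendar.

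**Inputs**
- Distribution on the last Friday of each month, for the prior month's data (DSMB Review).
- Sponsor review at the beginning of each month, taken here as day 1 (Sponsor Review).
- Enrollment of at least 6 patients monthly (Benchmarks), or 50 over one year, which is 50/12 = 4.17 per month (Protocol Summary). The two rates differ, so both are used as a range.
- Equal arms, 25 and 25 (Power Calculation).
- Mean month length 365.25/12 = 30.4375 days.

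**1. Wait if the report covers the preceding calendar month**

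For an event on day k of a month with L days, and a report on day d of the next month:

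wait = (L − k) + d

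The last Friday can fall on any date from the 22nd (possible only in a 28-day February) to the 31st.

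- Event on the last day (k = L): wait = d, so 22 to 31 days.
- Event on the 1st (k = 1): wait = L − 1 + d. Longest: 31 − 1 + 31 = 61 days, for example 1 December 2019 to Friday 31 January 2020. Shortest: 31 − 1 + 22 = 52 days, for example 1 January 2019 to Friday 22 February 2019.
- Averaged over every day of 2018 to 2020: 42.2 days. Enumerating 2000 to 2399 gives the same limits and the same mean to one decimal.

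These waits run to distribution only. The DSMB's own review time comes on top.

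**2. Wait if the report runs to the day it is sent**

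The longest wait is then the gap between successive last Fridays, which is 28 or 35 days depending on the month.

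**3. Lag behind the Sponsor's own review**

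d − 1 = 21 to 30 days, that is, three to four weeks.

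**4. Comparison with the other recipients**

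| Recipient | Limit for a serious event |
|---|---|
| IRB | 7 days from awareness |
| FDA | 7 days if fatal or life threatening, otherwise 15 |
| NICHD, OHRP | one month after IRB receipt: 7 + 30 or 31 = about 37 to 38 days from awareness |
| DSMB, prior-month reading | 22 to 61 days from the event |
| DSMB, to-date reading | at most 28 or 35 days from the event |

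**5. Women enrolled in the interval**

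number = monthly rate × wait / 30.4375

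- 61 days: 6 × 61/30.4375 = 12.0; 4.17 × 61/30.4375 = 8.4.
- 35 days: 6 × 35/30.4375 = 6.9; 4.17 × 35/30.4375 = 4.8.

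These counts cover both arms. About half would be in the device arm: roughly 4 to 6 women at 61 days, and 2 to 3 at 35 days.

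**The case against.** The strongest reply is proportionality. Each participant has two examinations within 10 minutes, the device is described as Class 1 low risk, results do not enter clinical care, and the trial has 50 patients. The IRB hears of serious events within a week, the FDA within one week or 15 days, and the FDA section itself provides for withdrawal of IRB approval. Monthly DSMB review can be defended in that setting. This stands, and it limits how much weight the point can carry.

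Three stronger readings are tempting, and the documents do not support them.

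- *The DSMB is the last body to be told.* This is not true in general. NICHD and OHRP may hear as late as about 37 to 38 days after awareness, while a late-month event reaches the DSMB in 22 to 31 days. On the to-date reading, the DSMB's 35-day maximum also falls inside that limit.
- *The delay is 61 days.* That is the extreme of one reading. The mean on that reading is about 42 days, and the other reading stops at 35.
- *The DSMB has no faster route at all.* A detailed monitoring plan goes to the IRB and a monitoring plan goes to NICHD. Neither is among the documents, and either might contain one. The institutions mentioned under Sponsor Review are also undefined and could be meant to include the DSMB. But the DSMB is not named there, no time limit is attached, and that review is itself monthly.

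The power to stop at any time does not answer the point. It is an authority, and the DSMB cannot use it on an event it has not heard about.

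**Conclusion.** The point holds as a minor safety improvement. The protocol describes one route to the DSMB, a monthly email sent three to four weeks after the Sponsor has reviewed the same data, and it specifies no individual notice of serious events to the body that must judge continuation. The wait is 22 to 61 days (mean about 42) on the prior-month reading and at most 28 or 35 days on the to-date reading. Even 28 days exceeds the IRB and FDA limits for serious events. At the 61-day extreme, about 8 to 12 more women would be enrolled across both arms.

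This assumes that the prior month means the preceding calendar month, that enrollment is even over time and split equally between arms, that awareness comes on the day of the event, and that no plan outside these documents gives the DSMB earlier notice. A reader might infer that women go unprotected in the interval. The documents do not support that, because the IRB is told within a week and can withdraw approval.

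**What to change.** Three changes of wording in the Data and Safety Monitoring Plan:

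1. Send the DSMB document together with the Sponsor's start-of-month review, in place of the last Friday.
2. Send the DSMB a de-identified copy of each serious adverse event report when it goes to the IRB (one week), and of each unanticipated problem report on its existing two-week IRB clock. Unexpected events that are neither serious nor unanticipated problems can stay in the monthly document, since no individual report is described for them.
3. State one data cut-off for the monthly document.

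If the separate monitoring plan already provides an expedited route, cite it in the DSMB Review section.

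The cost is small: a de-identification step for each copied report and a few extra emails. No new data collection is needed, and the sample size and analysis are unaffected.
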